8.1 Adverse Events

An AE is defined as any untoward medical occurrence in a clinical investigation patient administered a pharmaceutical product, which does not necessarily have a causal relationship with this treatment. An AE can therefore be any unfavorable and/or unintended sign (including an abnormal laboratory finding), symptom, or disease temporally associated with the use of an investigational medicinal product, whether or not related to the investigational medicinal product. All AEs, including observed or volunteered problems, complaints, or symptoms, are to be recorded on the appropriate eCRF.

AEs, which include clinical laboratory test variables, will be monitored and documented from the time of informed consent. Patients should be instructed to report any AE that they experience to

the Investigator, whether or not they think the event is due to study treatment. Beginning at screening, Investigators should make an assessment for AEs at each visit and record the event on the appropriate AE eCRF.

Wherever possible, a specific disease or syndrome rather than individual associated signs and symptoms should be identified by the Investigator and recorded on the eCRF. However, if an observed or reported sign or symptom is not considered a component of a specific disease or syndrome by the Investigator, it should be recorded as a separate AE on the eCRF. Additionally, the condition that led to a medical or surgical procedure (eg, surgery, endoscopy, tooth extraction, or transfusion) should be recorded as an AE, not the procedure itself.

Any medical condition already present at screening should be recorded as medical history and not be reported as an AE unless the medical condition or signs or symptoms present at screening changes in severity, frequency, or seriousness at any time during the study. In this case, it should be reported as an AE.

Clinically significant abnormal laboratory or other examination (eg, ECG) findings that are detected during the study or are present at screening and significantly worsen during the study should be reported as AEs, as described below. The Investigator will exercise his or her medical and scientific judgement in deciding whether an abnormal laboratory finding or other abnormal assessment is clinically significant. Clinically significant abnormal laboratory values occurring during the clinical study will be followed until repeat tests return to normal, stabilize, or are no longer clinically significant. Abnormal test results that are determined to be an error should not be reported as an AE. Laboratory abnormalities or other abnormal clinical findings (eg, ECG abnormalities) should be reported as an AE if any of the following are applicable:

- If an intervention is required as a result of the abnormality;
- If action taken with the study drug is required as a result of the abnormality; or
- Based on the clinical judgement of the Investigator.

8.1.1 Adverse (Drug) Reaction

All noxious and unintended responses to a medicinal product related to any dose should be considered an adverse drug reaction. “Responses” to a medicinal product means that a causal relationship between a medicinal product and an AE is at least a reasonable possibility (ie, the relationship cannot be ruled out).

8.1.2 Unexpected Adverse Drug Reaction

An Unexpected Adverse Drug Reaction is defined as an adverse reaction, the nature or severity of which is not consistent with the applicable product information.

8.1.3 Assessment of Adverse Events by the Investigator

The Investigator will assess the severity (intensity) of each AE as mild, moderate, or severe, and will also categorize each AE as to its potential relationship to study drug using the categories of Yes or No.

Assessment of severity

The severity of all AEs should be graded according to the CTCAE version 5.0. For those AE terms not listed in the CTCAE, the following grading system should be used:

- CTCAE Grade 1: Mild; asymptomatic or mild symptoms; clinical or diagnostic observations only; intervention not indicated;
- CTCAE Grade 2: Moderate; minimal local or noninvasive intervention indicated; limiting age-appropriate instrumental activities of daily living;
- CTCAE Grade 3: Severe or medically significant but not immediately life-threatening; hospitalization or prolongation of hospitalization indicated; disabling; limiting self-care activities of daily living;
- CTCAE Grade 4: Life-threatening consequences; urgent intervention indicated; and
- CTCAE Grade 5: Death related to the AE.

Causality assessment

The relationship of an AE to the administration of the study drug is to be assessed according to the following definitions:

No (unrelated, not related, unlikely to be related) – The time course between the administration of study drug and the occurrence or worsening of the AE rules out a causal relationship and another cause (concomitant drugs, therapies, complications, etc) is suspected.

Yes (possibly, probably, or definitely related) – The time course between the administration of study drug and the occurrence or worsening of the AE is consistent with a causal relationship and no other cause (concomitant drugs, therapies, complications, etc) can be identified.

The definition implies a reasonable possibility of a causal relationship between the event and the study drug. This means that there are facts (evidence) or arguments to suggest a causal relationship.

The following factors should also be considered:

- The temporal sequence from study drug administration;

The event should occur after the study drug is given. The length of time from study drug exposure to event should be evaluated in the clinical context of the event.

- Underlying, concomitant, intercurrent diseases;

Each report should be evaluated in the context of the natural history and course of the disease being treated and any other disease the patient may have.

- Concomitant drug;

The other drugs the patient is taking or the treatment the patient receives should be examined to determine whether any of them might be recognized to cause the event in question.

- Known response pattern for this class of study drug;

Clinical and/or preclinical data may indicate whether a particular response is likely to be a class effect.

- Exposure to physical and/or mental stresses; and

The exposure to stress might induce adverse changes in the recipient and provide a logical and better explanation for the event.

- The pharmacology and pharmacokinetics of the study drug.

The known pharmacologic properties (absorption, distribution, metabolism, and excretion) of the study drug should be considered.

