3.1.4.1 Definition of dose-limiting toxicities

DLTs are defined as toxicities occurring **only** within Cycle 1 (ie, the approximately 12-week [84-day] period that includes 2 administrations of the study drug given 4 weeks apart [including the 4-week Safety Follow-Up Period after Dose 1]). DLTs include ≥ 1 of the following:

- Study drug-related SAE in at least 1 patient in 1 cohort;
- Severe study drug-related AE in at least 2 patients in 1 cohort;
- Any death not clearly due to the underlying disease or extraneous causes;
- Development of severe renal failure (estimated glomerular filtration rate [eGFR] <30 mL/min) or a drop of >40 mL/minute in eGFR;
- Any seizure activity that is considered to be study drug-related;
- Grade 3+ thrombocytopenia with bleeding;
- Recurrent (defined in this study as occurring after >1 dose of CAM-H2 during Cycle 1) Grade 3 or 4 thrombocytopenia;
- Grade 4+ neutropenia or thrombocytopenia >7 days;
- Recurrent (defined in this study as occurring after >1 dose of CAM-H2 during Cycle 1) Grade 3 or 4 anemia and/or neutropenia;
- Recurrent (defined in this study as occurring after >1 dose of CAM-H2 during Cycle 1) Grade 3 or 4 non-hematological toxicities as listed in the Common Terminology Criteria for Adverse Events (CTCAE) version 5.0;
- An alanine aminotransferase (ALT) or aspartate aminotransferase (AST) $>3 \times$ upper limit of normal (ULN) accompanied by a total bilirubin of $>2 \times$ ULN (Hys Law);
- Grade 3 or 4 fatigue for >1 week;
- Grade 3 or 4 electrolyte abnormalities that last >72 hours or any Grade 3 or 4 electrolyte abnormalities associated with clinical signs and symptoms of any duration;
- For patients with hepatic metastases, AST or ALT $>8 \times$ ULN or AST or ALT $>5 \times$ ULN for ≥ 14 days;
- An absorbed dose to the kidneys >23 Gy;
- An absorbed dose to the bone marrow >2 Gy; or
- Other clinically significant changes in vital signs, clinical laboratory tests, ECGs, or other safety parameters deemed as a significant safety concern by the Investigator.

All AEs of the specified grades will count as DLTs, except those that are clearly and incontrovertibly due to disease progression or extraneous causes.

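### The two causality categories in Section 8.1.3 leave an event with plausible timing and another identifiable cause unclassified, and the Yes condition contradicts its own label and Section 8.1.1

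*Combined protocol and SAP*

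**What the plan says.** Section 8.1.3 states that the investigator "will also categorize each AE as to its potential relationship to study drug using the categories of Yes or No". There is no third category.

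- **Yes.** The label reads "Yes (possibly, probably, or definitely related". The operative condition is that the time course "is consistent with a causal relationship and no other cause (concomitant drugs, therapies, complications, etc) can be identified".
- **No.** The label reads "No (unrelated, not related, unlikely to be related". The operative condition is that the time course "rules out a causal relationship and another cause (concomitant drugs, therapies, complications, etc) is suspected".
- **Sentence after the definitions.** "The definition implies a reasonable possibility of a causal relationship between the event and the study drug".

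Two other sections set an attribution standard. Section 8.1.1 treats an event as an adverse drug reaction when a causal link "is at least a reasonable possibility (ie, the relationship cannot be ruled out". Section 3.1.4.1 counts events of the listed grades as DLTs "except those that are clearly and incontrovertibly due to disease progression or extraneous causes".

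Relatedness is then used in these places:

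- Section 3.1.4.1: three DLT items (a related SAE, a related severe AE in two patients of a cohort, a related seizure).
- Section 3.1.5.1: the halt after one related SAE or two related severe AEs, the lifting of that halt if the relatedness assessment changes, and the halt after two related DLTs in a cohort.
- Section 3.1.1.2: a patient who cannot complete the cycle is replaced if the AE is unrelated and is not replaced if it is related.
- Section 8.3: reporting of SAEs later than 30 days after the last dose.
- Section 9.2.3: the tables of TEAEs by relationship.

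**The concern.** The two conditions are not complements. Each joins a statement about timing to a statement about other causes, so the mixed cases fall between them. One mixed case, plausible timing with a competing cause, is easy to meet in this trial. Patients have refractory advanced disease, asymptomatic brain metastases are allowed, and thyroid blockers, premedication, saline and amino acids are given with each CAM-H2 administration. A seizure in a patient with brain metastases is an example: another cause can readily be named, yet timing may not exclude the study drug.

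An investigator faced with such an event must still enter Yes or No. The text supports either answer, so sites may differ. If the answer is No, the event leaves the relatedness-based DLT items and halts. If it also prevented the patient from completing the cycle, the patient is replaced and so drops out of the cohort used for the escalation decision.

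**Working it through.** **1. Are the categories exhaustive?** Cross timing with the presence of another cause:

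| Time course | Other cause | Category met |
|---|---|---|
| consistent | none identified | Yes |
| consistent | present | neither |
| rules out causation | none identified | neither |
| rules out causation | present | No |

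Two of the four combinations have no category. The second row is the one that matters in practice.

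**2. Are the standards consistent?** Four standards stand side by side:

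- Yes condition, 8.1.3: no other cause identifiable (demanding).
- Yes label and following sentence, 8.1.3: possible, or a reasonable possibility (lenient).
- 8.1.1: cannot be ruled out (lenient).
- 3.1.4.1, graded events: counted unless clearly and beyond dispute due to something else (most inclusive).

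The No category has the mirror-image problem. Its label takes in unlikely events, but its condition requires timing to exclude causation.

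**3. How much of the DLT definition depends on this field?** Section 3.1.4.1 has 17 items, and three carry a relatedness qualifier. That leaves 17 − 3 = 14, including the renal, hematological, hepatic, fatigue, electrolyte and absorbed-dose items. Death has its own attribution test, and the last item lets the investigator count any other significant safety concern. The item for recurrent Grade 3 or 4 non-hematological toxicity needs an event after more than one dose. A single such event outside the specific renal, hepatic, fatigue and electrolyte items therefore becomes a DLT only through a relatedness item or the investigator-concern item.

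**4. Size, as an upper illustration.** The documents give no figure on this point, so there is none to reproduce. Let p be the true per-patient DLT rate and m the share of DLTs coded No. Both are assumptions. The observed rate is q = p(1 − m). Under Section 3.1.4.2 a level is passed with 0/3 DLTs, or with 1/3 followed by 0/3:

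P(escalate) = (1 − q)³ + 3q(1 − q)² × (1 − q)³

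At p = 0.33, m = 0: 0.67³ = 0.301; 3 × 0.33 × 0.67² = 0.444; 0.301 + 0.444 × 0.301 = 0.434.

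At p = 0.33, m = 0.50, q = 0.165: 0.835³ = 0.582; 3 × 0.165 × 0.835² = 0.345; 0.582 + 0.345 × 0.582 = 0.783.

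| p | m = 0 | m = 10% | m = 25% | m = 50% |
|---|---|---|---|---|
| 0.20 | 0.709 | 0.752 | 0.814 | 0.906 |
| 0.33 | 0.434 | 0.500 | 0.605 | 0.783 |
| 0.50 | 0.172 | 0.234 | 0.351 | 0.600 |

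If p is read instead as the per-patient rate of related SAEs, the chance that the one-SAE halt triggers in a cohort of three is 1 − (1 − q)³. At p = 0.33 this is 0.699, 0.653, 0.574 and 0.418 for m = 0, 10%, 25% and 50%.

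The escalation figures assume that every DLT arises through a relatedness item, which step 3 shows is not so. They bound the effect for a given p and m and do not estimate it. They also leave out the replacement of patients.

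**The case against.** The strongest reply is that no under-count is shown. An event in the gap cannot properly be coded No either, because timing does not exclude causation. The label under Yes, the reasonable-possibility sentence and Section 8.1.1 all lean towards Yes. Section 8.1.3 also asks the investigator to weigh disease course, other drugs, class effects and pharmacology, which is clinical judgement and not automatic exclusion. An identified cause is narrower than a conceivable one. This stands: the direction of error is not fixed by the text. The possibility of divergent coding remains.

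Second, most DLT items do not depend on the field. The kidney is the predicted dose-limiting organ (Section 1.3.2), and its eGFR and absorbed-dose items need no Yes. The attribution sentence in Section 3.1.4.1 protects the graded items. This also stands and limits the reach. It does not close the gap, because that sentence speaks of specified grades while the related-SAE and seizure items have a relatedness qualifier and no grade.

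Third, there are other checks. Investigator Safety Reports list all AEs (Section 3.1.4), the Medical Monitor reviews data continuously, and the SRC Charter, which is not among the documents, may address attribution (Section 3.1.5.1). These reduce the risk but do not define the category.

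A reader might infer that most adverse events in this population fall in the gap. The documents give no figure that supports this.

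**Conclusion.** The point holds as a defect in the definitions. Section 8.1.3 offers two categories that do not cover all events, and the Yes condition contradicts its own label, the sentence that follows it and Section 8.1.1. Sites may code the affected events differently. Those coded No could be missed in three of 17 DLT items, in the relatedness-based halts, in the replacement rule and in late SAE reporting.

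A reader might go further and infer that DLTs will be under-counted and the MTD biased upward. The documents do not support that: gap events are unclassified and not assigned to No, 14 DLT items do not use the field, and the graded ones have their own attribution sentence. Nor is 0.43 to 0.78 the expected effect in this trial. It needs a true DLT rate of 33%, every DLT dependent on relatedness, and half of them coded No. With 10% or 25% coded No the figure is 0.50 or 0.61, and all of these are upper illustrations on assumed inputs.

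**What to change.** Rewrite the two definitions in Section 8.1.3 so that they are exhaustive, mutually exclusive and consistent with Section 8.1.1:

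- Delete the Yes condition that no other cause can be identified.
- Define Yes as a reasonable possibility of a causal relationship, one that cannot be ruled out, even if another cause is also possible.
- Define No as no reasonable possibility of a causal relationship.
- Reconcile the label under No. An event judged unlikely but not excluded would be No by the present label and Yes by the Section 8.1.1 standard. Either drop the word unlikely or say which events it covers.
- State that this one standard governs relatedness in the DLT items that use it, the halts and their lifting, replacement, and SAE reporting. State also how it sits beside the separate attribution sentence for graded events in Section 3.1.4.1.

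The edit is a few sentences and changes no dose, threshold or assessment. The cost is that more events will be coded as related. Because one related SAE is a DLT item and also triggers a pause, this may mean some more DLTs and dosing pauses. The documents do not allow the number to be estimated.

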8.1.4 Adverse Events of Special Interest

The Investigator will monitor each patient for clinical and laboratory evidence for adverse events of special interest (AESIs), including renal failure and myelodysplastic syndrome, during the patient's participation in this study.

The Investigator will assess and record any additional information on the AESI in detail on an AE form which must be submitted within 24 hours of awareness of the event.

During the course of the study, additional AESIs may be identified by the Sponsor.

AESIs must be recorded in the eCRF.

8.2 Serious Adverse Events

An AE or adverse reaction is considered serious if, in the view of either the Investigator or Sponsor, it results in any of the following outcomes:

- Death;
- A life-threatening AE;

Note: An AE or adverse reaction is considered "life-threatening" if, in view of either the Investigator or Sponsor, its occurrence places the patient at immediate risk of death. It does not include an event that, had it occurred in a more severe form, might have caused death.

- Requires hospitalization or prolongation of existing hospitalizations;

Note: Any hospital admission with at least 1 overnight stay will be considered an inpatient hospitalization. An emergency room or urgent care visit without hospital admission will not be recorded as an SAE under this criterion, nor will hospitalization for a procedure scheduled or planned before signing of informed consent, or elective treatment of a pre-existing condition that did not worsen from baseline. However, unexpected complications and/or prolongation of hospitalization that occur during elective surgery should be recorded as AEs and assessed for seriousness. Admission to the hospital for social or situational reasons (ie, no place to stay, live too far away to come for hospital visits, respite care) will not be considered inpatient hospitalizations.

- A persistent or significant disability/incapacity or substantial disruption of the ability to conduct normal life functions;

- A congenital anomaly/birth defect; or
- An important medical event.

Note: Important medical events that do not meet any of the above criteria may be considered an SAE when, based upon appropriate medical judgement, they may jeopardize the patient and may require medical or surgical intervention to prevent 1 of the outcomes listed above. Examples of such medical events include allergic bronchospasm requiring intensive treatment in an emergency room or at home, blood dyscrasias or convulsions that do not result in inpatient hospitalizations, or the development of drug dependency.

Note: Events of progression of a patient's underlying cancer, as well as events clearly related to the progression of a patient's cancer (signs/symptoms of progression) should not be reported as an SAE unless the outcome is fatal during the study or within the safety reporting period. If the event has a fatal outcome during that timeframe, the event of Progression of "Type of Cancer" must be recorded as an SAE with CTCAE Grade 5 (fatal) outcome indicated. Diagnosis of progression of disease or hospitalization due to signs and symptoms of disease progression alone should not be reported as an SAE.

8.3 Serious Adverse Event Reporting – Procedures for Investigators

Initial reports

All SAEs occurring from the time of informed consent until 30 days following the last administration of study drug must be reported to Medpace Clinical Safety within 24 hours of the knowledge of the occurrence. After the reporting window, any SAE that the Investigator considers related to the study drug must be reported to the Medpace Clinical Safety or the Sponsor/designee. All SAEs related to the study drug and/or study procedures, as determined by the Investigator, must also be reported to Medpace Clinical Safety within 24 hours of the knowledge of the occurrence.

To report the SAE, complete the SAE form electronically in the electronic data capture (EDC) system for the study. When the form is completed, Medpace Safety personnel will be notified electronically by the EDC system and will retrieve the form. If the event meets serious criteria and it is not possible to access the EDC system, send an email to Medpace Safety at [contact] or call the Medpace SAE reporting line (telephone number listed [below](#)), and fax/email the completed paper SAE form to Medpace (contact information listed in [Section 8.6](#)) within 24 hours of awareness. When the EDC system becomes available, the SAE information must be entered within 24 hours of the system becoming available.

Follow-up reports

The Investigator must continue to follow the patient until the SAE has subsided or until the condition becomes chronic in nature, stabilizes (in the case of persistent impairment), or the patient dies.

Within 24 hours of receipt of follow-up information, the Investigator must update the SAE form electronically in the EDC system for the study and submit any supporting documentation (eg, patient discharge summary or autopsy reports) to Medpace Clinical Safety via fax or email. If it is not possible to access the EDC system, refer to the procedures outlined above for initial reporting of SAEs.

8.4 Pregnancy Reporting

If a patient becomes pregnant during the study or within the Safety Follow-Up Period defined in the protocol, the Investigator is to stop dosing with study drug(s) immediately and the patient should be withdrawn from the study. ET Visit procedures should be implemented at that time.

A pregnancy is not considered to be an AE or SAE; however, it must be reported to Medpace Clinical Safety within 24 hours of knowledge of the event. Medpace Clinical Safety will then provide the Investigator/site the Exposure In Utero (EIU) form for completion. The Investigator/site must complete the EIU form and fax/email it back to Medpace Clinical Safety.

If the female partner of a male patient becomes pregnant while the patient is receiving study drug or within the Safety Follow-Up Period defined in the protocol, the Investigator should notify Medpace Clinical Safety as described above.

The pregnancy should be followed until the outcome of the pregnancy, whenever possible. Once the outcome of the pregnancy is known, the EIU form should be completed and faxed/mailed to Medpace Clinical Safety. If the outcome of the pregnancy meets the criteria for immediate classification as an SAE (ie, postpartum complication, spontaneous abortion, stillbirth, neonatal death, or congenital anomaly), the Investigator should follow the procedures for reporting an SAE.

